## **1. Trial objectives**

The primary objective of the DISC trial is to investigate whether collagenase injection followed by manipulation is non-inferior to limited fasciectomy surgery for the correction of Dupuytren's contracture of the hand. The primary endpoint on which assessment of non-inferiority will be based is the patient reported scores for part two of the Patient Evaluation Measure (PEM) at 12 months post treatment. Secondary objectives are;

- To investigate if remote measurement of extension deficit using photographs is as good as goniometric measurements in clinic to determine recurrence (Photography sub study).
- To investigate whether the correction achieved after Collagenase injection or surgical correction is maintained to 5 years (if justified by findings from the analysis at 1 year and 2 years).

This analysis plan details the analyses that will be implemented to answer the first two objectives. Analysis of longer term follow up data will be specified in a separate plan if a longer term study is conducted

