### 5.6.1 Recurrence

Recurrence at 6 months is defined as a change in extension deficit (measured as passive extension) of the reference joint of 6° or greater between 3 and 6 months post treatment. Recurrence at 12 months is defined as a change in extension deficit (measured as passive extension) of 20° or greater between 3 and 12 months post treatment [6]. This definition will be used to compare recurrence in each arm at 6 and 12 months post treatment.

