#### **8.4.7 Recurrence**

Recurrence will be defined in a binary manner (recurred or not recurred) at 6, 12 and 24 months post-treatment. Recurrence at the 6 month follow up is defined as an increase in passive extension deficit of the reference joint of 6° since the 3 month post treatment follow up. Recurrence at 12 and 24 months is defined as an increase in passive extension deficit of the reference joint of 20° since the 3 month post treatment follow up. These binary outcomes will be modelled using mixed effect logistic regression models adjusting for study reference joint (MCP or PIP), study reference digit, baseline PEM score and baseline passive extension measurement as fixed effects with centre as a random effect. These models will include all participants for whom the relevant (i.e. month 6 or month 12) binary indicator of recurrence can be derived using the available data. If perfect prediction occurs due to empty strata at some covariate combinations, then participants with study reference digit indicated as middle, index or thumb will be pooled so that reference digit becomes a three category covariate (little, ring, other). If the issue persists, then the term for study reference digit will be dropped from the model. If the baseline PEM score and/or baseline passive extension measurement is missing, then they will be imputed using predicted values via regression of the observed values on observed baseline MHQ scores and reference joint (MCP or PIP). If the MHQ score is also missing, then missing baseline PEM scores and/or baseline passive extension measurements will be imputed using predicted values via regression of the observed values on the observed baseline URAM scores and reference joint. If baseline URAM score is also missing then missing baseline PEM scores and/or baseline passive extension measurements will be imputed with the reference joint strata specific means. For both analyses, the estimated odds ratios for allocation (and two-sided 95% CIs) will be reported. This model will also be used to derive the absolute differences in risk of recurrence (together with two-sided 95% CIs) at representative values of the covariates (mean of the continuous covariates, both levels of reference joint, two levels of reference digit (ring or little) and marginalising over the centre random effects). We will also test composite null hypotheses about the absolute difference in incidence of recurrence at 12

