### 8.7.1 Primary sub-study analysis

The primary sub-study analysis will investigate the agreement between the mean of the three measurements obtained using goniometer at baseline, and the measurement obtained using patient photographs at baseline (or patient photographs taken prior to treatment if baseline photos are unavailable). We will calculate separate 95% limits of agreement for the MCP and PIP joints of participants' reference digits. A range of plots will be used to assess the extent to which the assumptions of these analyses are met. If there is evidence of a relationship between the differences of the two measurements and their magnitude, then steps will be taken to account for this relationship using regression methods [13]. The calculation of the limits of agreement assumes that the differences are approximately normally distributed. The extent to which this assumption is met will be assessed by inspection of a normal quantile-quantile plot. Should there be extreme departures from normality then a non-parametric approach will be used as described in [13]. The differences between the two types of measurement will be plotted against their average, with the estimated limits of agreement overlaid. The extent to which agreement varies by digit will be investigated by generating separate limits of agreement and plots by digit (little, ring or middle/index/thumb). If feasible, the extent to which agreement varies according to image quality will be investigated by generating separate limits of agreement and plots by image quality category. The extent to which time between measurements explains variation in agreement will be explored by regressing the observed differences on the magnitude of the measurements (i.e. the average of the measurements obtained using each method) and the time elapsed between the two measurements.

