### 8.7.2 Secondary sub study analyses

Secondary analyses of the photography sub study will use similar techniques as described for the primary sub study analysis to assess the agreement between goniometric measurements and measurements obtained using participant photographs at the 3 and 6 month post treatment time points. Similar techniques will again be used to assess the agreement between baseline goniometric measurements and measurements obtained using photographs taken in clinic at baseline.

[figure not shown]

[figure not shown]

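### The photography sub-study is meant to judge photographs for determining recurrence, but plans only single-visit agreement at baseline, 3 and 6 months, so it addresses recurrence only indirectly

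*SAP*

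**What the plan says.** Section 1 states the objective as "To investigate if remote measurement of extension deficit using photographs is as good as goniometric measurements in clinic to determine recurrence" and commits the SAP to it: "This analysis plan details the analyses that will be implemented to answer the first two objectives". The sub-study is the second of these.

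Section 5.6.1 defines recurrence at 6 months as "a change in extension deficit (measured as passive extension) of the reference joint of 6° or greater between 3 and 6 months post treatment" and at 12 months as "a change in extension deficit (measured as passive extension) of 20° or greater between 3 and 12 months post treatment". Section 8.4.7 applies the same threshold at 24 months: "Recurrence at 12 and 24 months is defined as an increase in passive extension deficit of the reference joint of 20° since the 3 month" visit.

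The primary sub-study analysis (8.7.1) computes limits of agreement between the mean of three baseline goniometer readings and "the measurement obtained using patient photographs at baseline", with pre-treatment photographs as a fallback. The secondary analyses (8.7.2) apply the same technique to "measurements obtained using participant photographs at the 3 and 6 month post treatment time points", and to clinic photographs at baseline. Breakdowns by digit, image quality and time between the two readings subdivide or regress those same differences.

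Sections 5.10 and 8.7 describe the working goal as agreement, or interchangeability, of measurements and do not mention recurrence. Section 5.9 says the images yield active extension and flexion, and section 5.10 says participants take the same images.

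**The concern.** The objective concerns a classification based on change between two visits. The planned analyses concern one reading at one visit, and the primary one is made before treatment, when recurrence cannot yet exist. Acceptable limits at baseline could be taken as support for remote follow-up of recurrence, although neither the change nor the classification would have been examined.

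The result also bears on another part of the plan. Section 8.4.7 repeats the between-arm recurrence comparison with photograph measurements supplementing the goniometry, because much goniometry will be missing after remote follow-up. At 12 and 24 months that repeat analysis would use photograph values at visits where the plan checks no agreement.

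A second mismatch runs alongside the first. Recurrence is defined on passive extension, photographs give active extension, and sections 8.7.1 and 8.7.2 do not say which goniometric extension is compared.

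**Working it through.** **Coverage.** Planned agreement analyses set against the recurrence definition:

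| Needed to judge recurrence | Data scheduled (Table 1; 5.10) | Agreement analysis planned (8.7.1, 8.7.2) |
|---|---|---|
| Reading at 3 months (reference visit) | yes | yes |
| Reading at 6 months | yes | yes |
| Reading at 12 and 24 months | yes | no |
| Change from 3 to 6 months (6° rule) | yes | no |
| Change from 3 to 12 or 24 months (20° rule) | yes | no |
| Recurred or not, by each method | derivable | no |

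The supplemented analysis in 8.4.7 fills gaps in the treatment comparison. It does not compare the methods.

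**From single-visit agreement to agreement on change.** Let s be the SD of photograph minus goniometer at one visit, taken as equal at both visits, and r the correlation of that difference between the two visits.

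- Single-visit 95% limits: ±1.96 × s around the mean difference.
- SD of the method difference in change: s × √(2(1 − r)).
- Limits for change: ±1.96 × s × √(2(1 − r)).

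A constant offset cancels in a change, and so does any person-specific offset shared by both visits. Independent error adds. At r = 0.5 the two sets of limits are equal. Below 0.5 the limits for change are wider, and above it they are narrower.

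The SAP gives neither s nor r, so both are assumptions, shown over a range. For s = 7°, the single-visit limits are 1.96 × 7 = 13.7°. For change:

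- r = 0: 1.96 × 7 × √2 = 19.4°
- r = 0.5: 1.96 × 7 × √1 = 13.7°
- r = 0.8: 1.96 × 7 × √0.4 = 8.7°

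| Assumed s | Single-visit limits | Change, r = 0 | Change, r = 0.5 | Change, r = 0.8 |
|---|---|---|---|---|
| 5° | ±9.8° | ±13.9° | ±9.8° | ±6.2° |
| 7° | ±13.7° | ±19.4° | ±13.7° | ±8.7° |
| 10° | ±19.6° | ±27.7° | ±19.6° | ±12.4° |

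**Effect on the 6° rule.** If goniometry shows no change and the mean method difference is the same at both visits, the chance that photographs show 6° or more is 1 − Φ(6 / (s√(2(1 − r)))). At s = 7° the SD for change is 9.90°, 7.00° and 4.43° for r = 0, 0.5 and 0.8, so the chance is 27%, 20% and 9%. The same single-visit limits of ±13.7° therefore fit quite different classification performance.

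Separate limits at 3 and 6 months estimate s at each of those visits but not r. For 12 and 24 months the plan estimates neither.

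**The case against.** A reader might infer that the sub-study cannot answer its objective at all, or that its results say nothing about recurrence. The SAP does not support that. Section 8.7.2 tests agreement at 3 months, the reference visit for every recurrence definition, and at 6 months, itself a recurrence endpoint. With equal s and r of zero or more, the SD for change is at most s√2, so limits for change are at most 1.41 times the single-visit limits. Narrow limits would be real, if indirect, reassurance: single-visit limits inside 20/√2 = ±14.1° would keep limits for change inside ±20°. This stands, although it reaches 12 and 24 months only if s is the same there. The converse does not stand, because wide single-visit limits can go with narrow limits for change when r is high (s = 10°, r = 0.8: ±19.6° against ±12.4°).

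A reader might also infer that a change is always measured worse because it carries the error of two readings. That ignores shared offsets and holds only for r below 0.5. Nor can a particular loss of sensitivity for recurrence be claimed. It would need a distribution of goniometric change that the SAP does not give, and the answer moves greatly with that choice.

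Three practical objections remain. Sections 5.10 and 8.7 already give the working goal as agreement of measurements, so rewording section 1 would remove the contradiction without new analyses. That is a legitimate alternative. Recurrences with both methods at both visits may be few: if there were 10 and photographs found 7, the exact 95% CI for sensitivity would run from 35% to 93%. That argues for descriptive reporting, not for omission, and agreement on the 3 to 6 month change needs only data that 8.7.2 already uses. Finally, comparing active extension by both methods would not by itself answer an objective defined on passive extension. The fix below allows for this.

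**Conclusion.** The concern holds in a limited form. The SAP undertakes to say whether photographs are as good as goniometry for determining recurrence. It plans no analysis of agreement on change since 3 months, none of recurrence status, and none at 12 or 24 months, where the 20° rule applies. What is planned bears on recurrence only indirectly.

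The gap rests on the text alone. Its numerical size cannot be taken from the SAP. The limits above depend on assumed s and r and on equal s at both visits, and they show that single-visit limits may be too narrow or too wide for change. They do not show that photographs perform badly. The point concerns a secondary objective and leaves the primary PEM analysis and its non-inferiority conclusion untouched.

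**What to change.** In 8.7.2 add, for sub-study participants with both methods at both visits:

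- **Change.** Limits of agreement for the change in extension since 3 months at 6, 12 and 24 months, photograph minus goniometer, by joint.
- **Classification.** A 2×2 table of photograph-based change at the SAP's threshold (6° at 6 months, 20° at 12 and 24 months) against goniometric recurrence as the SAP defines it, on passive extension. Add a parallel table using active extension for both methods, to separate method error from the active/passive difference. Give sensitivity, specificity and kappa with CIs.

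Extend single-visit agreement to 12 and 24 months, and state in 8.7.1 and 8.7.2 which goniometric extension is compared. State that the baseline analysis supports single-visit agreement only. If the added analyses are not wanted, narrow the section 1 objective to agreement of measurements.

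The cost is SAP wording and a few tables from data already scheduled. The downside is precision: remote follow-up may leave few paired readings and few recurrences at 12 and 24 months, so the classification results should be reported as descriptive, with CIs.

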## **2. Design**

DISC is a multi-centre, parallel group, individually randomised controlled non-inferiority trial of collagenase injection and manipulation versus limited fasciectomy surgery for the treatment of Dupuytren's contracture. In addition to the main study, DISC contains a qualitative sub study and a photography sub study. This plan outlines the pre-specified analyses of the main trial and the photography sub study. Eligible and consenting patients will be randomised 1:1 to either collagenase injection and manipulation or limited fasciectomy surgery, using a secure randomisation service. Due to the nature of the interventions under investigation, it is not possible to blind clinicians or participants to their treatment allocation. Both treatments should be delivered within 18 weeks of randomisation (as per referral to treatment time), however where possible sites should deliver treatment within 12 weeks of randomisation. Participants will be followed up at 2 and 6 weeks post treatment and 3, 6, 12 and 24 months post treatment. A flow diagram illustrating the flow of participants through the study is presented in Appendix A.

## **3. Sample size**

The primary outcome for DISC is the score obtained for the 11 items in part two of the PEM at 12 months post treatment. Previous survey data collected from a representative sample of 880 patients with Dupuytren's Contracture showed the standard deviation of the scores for the 11 items in part 2 of

the PEM at baseline to be 22 points (unpublished). We estimate that a 6 point difference on the PEM at 12 months post-treatment is the threshold at which differences become relevant to the patient, and represents an appropriate non-inferiority margin. An effective sample size of 568 participants (284 per arm) is required to obtain 90% power to assess non-inferiority of collagenase based on the upper limit of a two sided 95% confidence interval (CI) (equivalent to a one-sided 97.5% CI) for the treatment difference ( $\delta = \text{collagenase} - \text{surgery}$ ) at 12 months post treatment, assuming a non-inferiority margin of 6 points and a standard deviation of 22 points. This calculation is based upon the sample size needed for 90% power in a one-sided independent samples t-test of size 2.5%, of  $H_0: \delta \geq 6$  vs  $H_1: \delta < 6$ , ignoring informative baseline covariates (reference joint and baseline PEM score). If  $\delta = 6$ , then we would expect the null hypothesis that collagenase is inferior to surgery to be rejected in 2.5% of hypothetical repetitions of the trial. If  $\delta = 0$ , then we would expect the null hypothesis that collagenase is inferior to surgery to be (correctly) rejected in 90% of hypothetical repetitions of the trial (assuming an analysis based on a one sided independent samples t-test of size 2.5%). Assuming 20% attrition at the 12 month follow up, the total target sample size is 710.

#### **4. Randomisation**

The randomisation sequence was designed by the study statistician and is accessed via telephone or the internet using a secure, central randomisation service hosted by Sealed Envelope Ltd. This will ensure adequate allocation concealment for the study. This service will record information to identify all potential participants and their eligibility to avoid inappropriate entry of patients into the trial. The research team at each study site will access the system to complete randomisation following participant consent and completion of baseline assessments. Access to the system for representatives at individual sites will be coordinated and controlled by the trial project team at YTU. Both participants and clinicians will not be blind to allocation. The randomisation system has been designed to allocate participants 1:1 to each of the two study treatment arms. The system uses block randomisation with randomly varying block sizes, stratified by reference joint (MCP or PIP). The actual allocation sequence has been generated using a randomly generated seed provided by a statistician not involved in the ongoing or final analysis of the study.

#### **5. Outcome data**

Outcome data will be collected using both participant and clinician completed CRFs at 8 different time points. A table summarising the data collection schedule is given in Appendix B.

##### **5.1 Patient Evaluation Measure**

The PEM [1] is a validated 19 item patient reported outcome measure comprised of three parts.

- Part 1 is comprised of 5 items which ask the participant about their experience of treatment and the care they received.

- Part 2 is comprised of 11 items which ask the participant about their hand's functionality and any pain they may experience.
- Part 3 is comprised of 3 items and provides an overall assessment of the participant's feelings about their hand condition and treatment.

The participant assigns each item an integer score between 1 and 7, where higher scores indicate worse outcomes/experiences. Participants complete the PEM at baseline, immediately prior to treatment delivery and at 3, 6, 12 and 24 months post treatment. Participants are instructed to complete the PEM with respect to the hand designated as the study reference hand. PEM data will be scored as follows.

#### **5.1.1 PEM - Hand Health Questionnaire (11 items)**

The primary outcome for DISC is the score obtained for the 11 items in Part 2 of the PEM, known as the Hand Health Questionnaire. The Hand Health Questionnaire will be scored as follows:

- Subtract 1 from all responses, so that each item has an integer score between 0 and 6.
- If the participant has fewer than three missing items in part 2, then the missing item(s) are imputed with the mean of the non-missing items. If the participant has more than two missing items then an overall score cannot be calculated and is considered missing.
- Sum the scores for the 11 items to obtain a raw score. This should be between 0 and 66.
- Calculate their percentage disability by generating a normalised score between 0 and 100. A higher score indicates greater disability.

#### **5.1.2 PEM – Hand Health and Overall Assessment Questionnaire (14 items)**

An overall score for the 14 items in parts 2 and 3 will also be calculated as follows:

- Subtract 1 from all responses, so that each item has an integer score between 0 and 6.
- If the participant has fewer than three missing items in part 2, and no missing items in part 3, then the missing item(s) in part 2 are imputed with the mean of the non-missing items in part 2. If the participant has more than two missing items in part 2, or any missing items in part 3, then an overall score is not calculated and is considered missing.
- Sum the scores for the 14 items to obtain a raw score. This should be between 0 and 84.
- Calculate their percentage disability by generating a normalised score between 0 and 100. A higher score indicates greater disability.

This score will only be calculated and reported for the four post treatment follow up time points. This is because some of the items in part 3 are not applicable to participants prior to treatment delivery.

### **5.1.3 PEM – Treatment Questionnaire (5 items)**

An overall score for the 5 items in part 1 will also be calculated as follows:

- Subtract 1 from all responses, so that each item has an integer score between 0 and 6.
- If the participant has one missing item in part 1, then this item is imputed with the mean of the 4 non-missing part 1 items. If the participant has more than one missing item, then an overall score cannot be calculated and is considered missing.
- Sum the scores for the 5 items to obtain the treatment questionnaire score. This should be between 0 and 30.

This score will only be calculated and reported for the four post treatment follow up time points. This is because the items in part 1 are not applicable to participants prior to treatment delivery.

## **5.2 Unité Rhumatologique des Affections de la Main Scale**

The URAM is a validated, 9 item, disease specific disability scale assessing the difficulty experienced by the participant in performing particular tasks or movements [2]. Each item is scored between 0 and 5 with higher scores indicating greater difficulty. Participants complete the URAM at baseline and 3, 6, 12 and 24 months post treatment.

- If more than two items are missing then an overall URAM score cannot be calculated and should be considered missing.
- If the participant has fewer than three missing items, then any missing items are imputed with the mean of the non-missing items. If a participant has more than two missing items, then an overall score is not calculated and is considered missing.
- The overall score is calculated by summing the scores for all nine items. The resulting score should be between 0 and 45 with higher scores indicating greater difficulties.

